We also tested an alternative dosing strategy in an effort to counteract these PK changes and demonstrated that obese women taking double the approved LNG EC dose normalized the PK profile to that of normal BMI women. Although a “take two” strategy could be rapidly implemented into clinical practice, we have no data on the resulting end-organ effects. Further studies are needed to document if PK normalization results in improved pharmacodynamic (PD) outcomes. Another alternative treatment strategy is to use a UPA-based EC instead. UPA is slightly more effective than LNG-based EC as it has a longer window of action (e.g. effective until LH peak vs. LH rise) [2]. However, published data demonstrate a possible decline in efficacy for obese women [4]. Detailed PK and PD studies for UPA have yet to have been performed in obese women but unpublished data from a colleague at Columbia University also demonstrated PK differences (*personal communication 4-2016*).

The overall goal of this research is to improve EC effectiveness and quality of clinical care for obese women. We hypothesize that increasing the dose of LNG- and UPA-based EC will normalize PK (specifically the time needed to reach a therapeutic drug level) and PD outcomes (follicle rupture) in obese women who weigh 80kg or greater. In this application we propose to expand our model for LNG- to UPA-based EC, assess the pharmacodynamic outcomes of these alternative dosing regimens (“take two”) in obese women and to assess the safety and acceptability of these regimens in this population.

Methods:

Study design: This is a 2-part study: Part 1 will be focused on LNG-EC and Part 2 will be focused on UPA-EC. Eligible women can take part in both aspects of the study and in no particular order. If they do choose to enroll

in both aspects of the study, then the screening visit does not need to be repeated unless it has been greater than 12 months since the original screening visit.

Part 1 LNG-EC is a randomized control trial. Part 2 UPA-EC is a randomized cross-over study with an additional non-randomized control arm.

This study will be conducted at Oregon Health & Science University (OHSU) in Portland, OR and a subcontract site, Eastern Virginia Medical School (EVMS) in Norfolk, Virginia. EVMS will be overseen by their own IRB.

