PK parameter analysis. UPA PK parameters will be generated by noncompartmental methods using WinNonLin (Pharsight, Mountain View, CA). Cmax and time to maximum Cmax will be observed values. Area under the curve (AUC) will be calculated from Time 0 to 120hr (AUC0-120) using the linear trapezoidal rule and then extrapolated to infinity which provide a more accurate calculation of drug clearance (Rowland 1980). Drug half-life (t1/2), oral clearance (CL), and volume of distribution (VD) will be generated using standard pharmacokinetic calculations ($t_{1/2} = 0.693/\lambda_z$ where λ_z is the terminal elimination rate constant; $CL = dose/AUC_{0-\infty}$; $VD = CL/\lambda_z$). Descriptive statistics will be generated for each parameter [mean (standard deviation)], concentration-time curves will be generated for all of the doses and their respective BMI groups. Depending on the normality of the data, parametric or nonparametric testing will be performed for each parameter between the normal and obese BMI ECx1 groups and paired statistics will be utilized to compare obese BMI ECx1 and ECx2.

We also plan to perform analyses to compare PD outcomes in obese users ingesting LNG and UPA, ECx1 and ECx2. UPA and LNG are the only two orally-dosed EC agents available on the market. A logical sub analysis is the comparison of the different dosing strategies to help guide future studies or even clinical management of orally-dosed EC in obese women if dose escalation appears effective. We will utilize the data collected in Aim 1 and 2. The proportion of women with a delay in follicular rupture (yes/no) in 4 different treatment regimens obtained in the trial in aim1 and 2 will be compared and test if there's significant difference

between LNG ECx2 and UPA LNG ECx2 using Chi-square test. Due to exploratory purpose of these analyses, the analysis will be descriptive but given the projected sample size (35 per group in Part 1 and 80 per group in Part 2) we will achieve more than 80% power with 5% of significance level to detect 23% difference in delay in follicular rupture. In addition, one of the secondary outcomes of time from treatment intake to follicular rupture will be compared among treatment groups using survival analysis.

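### The exploratory comparison of LNG ECx2 with UPA ECx2 is not randomised and shares women between groups, yet is tested by an unadjusted chi-square that ignores LH status at dosing

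*Combined protocol and SAP*

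**What the plan says.** - **The test.** After the PK paragraph of the Part 2 data analysis section, the plan compares the proportion with delayed rupture across the four regimens and tests for a difference "between LNG ECx2 and UPA LNG ECx2 using Chi-square test". No covariate or stratum is named. A survival comparison among treatment groups is added, also without covariates.
- **Its status.** The plan states: "Due to exploratory purpose of these analyses, the analysis will be descriptive". It nevertheless quotes "more than 80% power with 5% of significance level to detect 23% difference in delay in follicular rupture", with 35 LNG and 80 UPA women per group, and gives the purpose as "to help guide future studies or even clinical management of orally-dosed EC in obese women" if dose escalation appears effective.
- **Allocation.** Part 1 randomises between LNG 1.5 mg and 3 mg. Part 2 is a randomised cross-over within UPA. On joining the parts, the study design paragraph says: "Eligible women can take part in both aspects of the study and in no particular order". The Part 2 sample size paragraph expects 40 women to enter Part 2 after Part 1.
- **LH.** The Background says of UPA that "it has a longer window of action (e.g. effective until LH peak vs. LH rise". Blood for LH is drawn and ultrasound done at every visit in both parts. Both analysis sections report LH level, follicle diameter and cycle day on the day of ingestion.
- **Adjustment elsewhere.** LH status is used only within a part: Fisher's exact test in Part 1, a plot in Part 2. Logistic regression (Part 1) and GEE (Part 2) serve only the ECx1 v ECx2 contrasts.

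**The concern.** The two randomised dose contrasts each have a route to adjustment. The one contrast between drugs, which has no protection from randomisation, has none. Women choose which part to join, and the share dosed before, during or after the LH surge may differ between parts. Since inhibition of rupture is expected to depend on that stage, a difference in stage could look like a drug difference or hide one.

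Two further faults attach to the same test. Women who take part in both parts contribute to both groups, so the observations are not independent. The yes/no outcome is also not defined for this comparison: Part 1 analyses absence of rupture, Part 2 a delay of at least 6 days.

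No primary result depends on this test. What is at stake is how far a p-value from it can support the stated use for future studies or clinical management.

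**Working it through.** **1. The plan's own power figure.** Inputs: 35 v 80, a 23-point difference, 5% (two-sided assumed). No base rate is given, so the figure cannot be fully reproduced. With pooled rate p̄, s0 = √[p̄(1−p̄)(1/35+1/80)] and s1 = √[p1(1−p1)/35 + p2(1−p2)/80], power = Φ[(0.23 − 1.96·s0)/s1].

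Example, LNG 10% v UPA 33%: p̄ = (3.5+26.4)/115 = 0.26, s0 = 0.0889, s1 = 0.0730, power = Φ(0.76) = 77.7%.

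| LNG v UPA | Power |
|---|---|
| 5 v 28% | 86.3% |
| 10 v 33% | 77.7% |
| 20 v 43% | 67.4% |
| 40 v 63% | 63.0% |
| 50 v 73% | 66.5% |
| 67 v 90% | 82.6% |

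With LNG the lower group, the claim of over 80% holds only towards the extremes. The point here does not depend on it.

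**2. Effect of an LH imbalance on the crude test.** The documents give no inhibition rate by LH status, so the rates are assumptions: no drug difference, 50% inhibition if dosed before the surge, 5% after. If a share s is dosed before the surge, the expected rate is p = 0.50s + 0.05(1−s). The rejection rate is the exact binomial probability that the uncorrected chi-square exceeds 3.84 with 35 v 80 independent women.

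| Share before surge, LNG v UPA | Gap | Expected rates | Rejects |
|---|---|---|---|
| 70 v 70% | 0 | 36.5 v 36.5% | 4.9% |
| 75 v 80% | 5 | 38.8 v 41.0% | 5.5% |
| 70 v 80% | 10 | 36.5 v 41.0% | 7.2% |
| 60 v 80% | 20 | 32.0 v 41.0% | 14.6% |
| 55 v 85% | 30 | 29.8 v 43.3% | 27.4% |

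**3. Does using LH status help?** This is a simulation (20,000 runs per scenario) with other assumed rates: 80% inhibition before LH rise, 10% after, no drug difference, 20% of UPA women dosed after LH rise. With 20, 30, 40 and 50% of LNG women dosed after LH rise, the crude test rejects 5, 11, 29 and 56% of the time. A Mantel-Haenszel test stratified by LH status stays at about 5%. With LH balanced and a true 23-point difference in each stratum (50 v 73%, 10 v 33%), power is 63% crude and 68% stratified, so stratifying costs no power in that scenario.

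**4. Overlap.** With 1:1 allocation, about 40 × ½ = 20 of the women in both parts would have had LNG ECx2. If all 20 also complete UPA ECx2 and outcomes correlate at ρ within woman, the null variance of the difference is p(1−p)[1/35 + 1/80 − 2·20ρ/(35·80)] = p(1−p)[0.0411 − 0.0143ρ]. The chi-square uses 0.0411. For an assumed ρ of 0.3 the true variance is 90% of that, and for ρ = 0.5 it is 83%. Positive correlation therefore makes the chi-square conservative and wastes information. It does not inflate false positives.

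**5. Sparse events.** In the 60 v 80% row, 0.40 × 35 = 14 LNG and 0.20 × 80 = 16 UPA women are dosed after the surge. At 5% inhibition, treating all 30 as independent, the chance of no event among them is 0.95^30 = 21%. An ordinary logistic LH coefficient would then be inestimable.

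**The case against.** The analysis is a labelled exploratory sub-analysis, and guidance for clinical management is mentioned only conditionally. This stands and limits the weight of the point. It does not remove confounding, and the plan still attaches a significance test and a power claim.

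Both parts use the same visit schedule, the same trigger of about 15 mm for dosing and the same obese eligibility criteria, and about 40 of the 80 UPA women are expected to come from Part 1. This also stands: LH status may be close to balanced, and small gaps do little harm. Chance imbalance is not an extra source of error, because the nominal 5% already allows for it.

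A reader might infer that the Background sentence on LH windows shows LH status to be a confounder here. It does not. It says that the drugs' effects differ by LH status, which is effect modification. Confounding also needs the LH mix to differ between parts, and the documents give no evidence of that. A single adjusted drug effect would average over the very difference the Background describes.

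A reader of the report could compare the regimens informally from the within-part LH summaries. That is a partial remedy, but no adjusted between-drug estimate is planned.

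**Conclusion.** The point holds at moderate weight. The LNG ECx2 v UPA ECx2 test is a non-randomised comparison of partly overlapping groups, analysed as if the groups were randomised and independent, without covariates that the trial already collects.

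The size of any bias is unknown. Under the assumed 50% and 5% inhibition rates, false-positive rates run from about 5.5% for a 5-point gap in LH stage to about 27% for a 30-point gap. These figures assume independent groups. A reader might take the upper figures as the plan's actual error rate. The documents do not support that, since they give neither an LH distribution nor inhibition rates by LH status, and the common dosing trigger argues against large gaps. Nor do they support reading the comparison as a confirmatory basis for clinical management.

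**What to change.** In the cross-drug paragraph of the Part 2 data analysis section:

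1. Define one yes/no outcome identically for LNG and UPA.
2. Replace the chi-square with a logistic GEE clustered on woman, with drug as the contrast, adjusted for LH status and leading follicle diameter on the dosing day and for weight, all fixed in advance. Define LH status from samples up to and including the dosing visit, so that later values affected by treatment do not enter it.
3. State in advance that LH status will be collapsed to two levels, or a penalised or stratified method used, if events are sparse.
4. Report the adjusted difference with a 95% interval, and show the results for each drug by LH status.
5. Label the comparison non-randomised and exploratory.

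The cost is SAP wording and one model, with no new data. Few events limit the model to these few covariates, and self-selection into the parts cannot be fully removed by adjustment.

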Study end will be at the onset of menses at the end of the treatment cycle (defined as two consecutive days of spotting/bleeding). We estimate up to 12 visits in the treatment cycles depending if delay in ovulation occurs. Subjects will have the option to undergo a washout cycle and participate in the studies detailed in Part 2; if they chose to do so, they will not have to undergo another screening visit or control cycle.

Procedure flow:

	Visit 0 (Screening Visit)	Treatment Cycle Starting Cycle 1 day 6-8
Consent, Screening tests and medical history	X	
blood draws	X	X
ultrasound		X
Study Medication & urine pregnancy test		X*
Total time	2 hour	30 min/visit

*Visit number study medication will be taken depends on ultrasound findings.

Data Analysis & Sample Size: All analyses will be performed on an intention-to-treat (ITT) basis. To demonstrate equality between treatment arms at baseline, we will compare participant demographics using two sample t-test or chi-square test, and descriptive statistics such as mean, median and percentages within each group will be reported. **The primary outcome analysis will compare the proportion of women with no follicular rupture (yes/no) between the treatment groups using a Chi-square test.** As mentioned previously, follicle rupture will be defined as the disappearance of or $>50\%$ reduction of size of the leading follicle [2,17].

Confirmation of the timing of ovulation will be supported by LH, P4, and E2 levels. If necessary, we will address any unanticipated imbalances between the treatment groups after randomization by adjusting for these confounders in analysis using a logistic regression. Descriptive statistics will be utilized to report LH and P levels [mean (standard deviation)], follicular diameter [median (range)], and cycle day [median (range)] on the day of EC ingestion during the treatment cycle within each group. Additionally, the proportion of inhibition of follicular rupture by LH status (no surge, start of LH surge, or after LH peak) [2,17] for each cycle will be compared between treatment groups using fisher's exact test. Mean LH, P4, and E2 levels over time will be plotted by treatment group. Time from treatment intake to follicular rupture will be assessed by a survival

analysis using Kaplan-Meier curve and log-rank test. All statistical analyses will be performed with the SAS version 9.4 (Cary, NC, USA).

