We believe that the difference between groups will be large (50% or greater) given that LNG ECx1 in obese women appears to be equivalent to placebo (normal ovulation) as well as the large PK differences we found in our preliminary studies. However, we have chosen a more conservative difference (30%) in which to base our sample size calculations to ensure we have the ability to capture a range of differences. A sample size of 62 will achieve 80% power to detect a 30% difference in the proportion of cycles that demonstrate inhibition of follicular rupture (yes/no) using a two-sided Z test with a 5% significant level assuming 90% rate of normal time to ovulation in LNG ECx1 dose group. **We plan to screen up to 80 women to account for screen failures and enroll a total of 70 women to account for drop out.**

Part 2 UPA-EC, obese BMI and a weight of 176 lbs or more and normal BMI and a weight of less than 176 lbs, randomized cross-over trial.

Specific Aim: To compare the pharmacokinetic parameters and pharmacodynamic profile of emergency contraception containing ulipristal acetate between obese and normal BMI women, and to determine if dose escalation improves how well it works in obese women.

Hypothesis: The peak drug level of UPA-EC is lower in obese women than in normal BMI women which adversely impacts the therapeutic effect and dose escalation will improve drug efficacy for obese women.

[figure not shown]

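### The claim of more than 80% power for LNG ECx2 against UPA ECx2 (35 v 80 women, 23 points) states no reference rate or direction and fails over most of the range, falling to about 63%.

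*Combined protocol and SAP*

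**What the plan says.** The passage is in Part 2, Data Analysis & Sample Size, after the PK parameter analysis. It plans to compare delay in follicular rupture across the four LNG and UPA regimens and to test for a difference "between LNG ECx2 and UPA LNG ECx2 using Chi-square test". The second label is evidently a slip for UPA ECx2. It then says "Due to exploratory purpose of these analyses, the analysis will be descriptive". The group sizes it projects are 35 women for each LNG regimen and 80 for each UPA regimen. For those sizes the power claim reads: "we will achieve more than 80% power with 5% of significance level to detect 23% difference in delay in follicular rupture". No event rate, direction or sidedness is attached to that figure.

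The only event rate in any of the document's power calculations is in Part 1, Data Analysis & Sample Size, which sizes Part 1 "assuming 90% rate of normal time to ovulation in LNG ECx1 dose group". In that section the investigators also write "We believe that the difference between groups will be large (50% or greater"), but "we have chosen a more conservative difference (30%) in which to base our sample size calculations".

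**The concern.** The variance of a proportion changes with its level, so 35 and 80 women do not give one power for a 23-point difference. They give a different power at each pair of rates. An unconditional figure is safe only if it holds at every plausible rate, and this one looked too high for a smaller arm of 35.

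The stakes are limited, because this comparison does not drive the sample size. However, the plan says it may inform later studies or even clinical management of oral EC in obese women. A reader who trusts the stated power could take a non-significant chi-square as good evidence against a 23-point difference when the chance of detecting one was nearer 63%.

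**Working it through.** **Inputs**
- n₁ = 35 (LNG ECx2), n₂ = 80 (UPA ECx2), difference 0.23, significance level 5%: from the power sentence.
- Two-sided, z = 1.96: assumed. A chi-square test on a 2×2 table is two-sided, and the other two-proportion calculations in the document are stated as two-sided.
- The groups are treated as independent, as the planned chi-square test does.
- Reference rate: not given, so it is varied. p₁ is the LNG ECx2 rate and p₂ the UPA ECx2 rate.

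**Formulas**
- Let p̄ = (35p₁ + 80p₂)/115, S₀ = √[p̄(1−p̄)(1/35 + 1/80)] and S₁ = √[p₁(1−p₁)/35 + p₂(1−p₂)/80].
- Pooled Z (the chi-square approximation): power = Φ[(0.23 − 1.96·S₀)/S₁].
- Unpooled Z: power = Φ[0.23/S₁ − 1.96].
- Arcsine: power = Φ[(2·asin√p₂ − 2·asin√p₁)/√(1/35 + 1/80) − 1.96].
- Exact: sum the binomial probabilities of all tables that the Pearson chi-square rejects.

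**Trying to reproduce the stated figure.** With no rate given it has no unique source. The only stated rate is Part 1's 90% normal ovulation on LNG ECx1, which is 10% inhibition. At 10% v 33%:
- p̄ = 0.26, S₀ = 0.0889, S₁ = 0.0730.
- Pooled: Φ[(0.23 − 0.1742)/0.0730] = 77.7%.
- Unpooled: Φ[3.149 − 1.96] = 88.3%.
- Arcsine: 81.7%. Exact: 79.3%.

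So two methods exceed 80% and two just miss, at a rate that belongs to a different LNG arm.

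**The named pair at the rate Part 1 implies.** 10% plus the 30-point sizing difference gives 40% on LNG ECx2. At 40% v 63%:
- p̄ = (14 + 50.4)/115 = 0.56, S₀ = 0.1006, S₁ = 0.0988.
- Pooled: Φ[(0.23 − 0.1972)/0.0988] = 63.0%.
- Unpooled: Φ[2.327 − 1.96] = 64.3%.
- Arcsine: 63.0%. Exact: 63.0%.

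This is a scenario, not a stated assumption. Part 1's endpoint is the "proportion of women with no follicular rupture (yes/no) between the treatment groups", whereas Part 2's is a delay of at least 6 days.

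**Across rates, UPA 23 points higher (power, %)**

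| LNG ECx2 rate | Pooled | Unpooled | Arcsine | Exact |
|---|---|---|---|---|
| 10% | 77.7 | 88.3 | 81.7 | 79.3 |
| 20% | 67.4 | 74.9 | 69.9 | 68.6 |
| 30% | 63.1 | 67.3 | 64.3 | 64.2 |
| 40% | 63.0 | 64.3 | 63.0 | 63.0 |
| 50% | 66.5 | 65.0 | 65.5 | 65.9 |
| 60% | 74.2 | 69.7 | 72.7 | 74.7 |
| 70% | 86.8 | 79.6 | 86.8 | 88.7 |
| Rates with power under 80% | 8.6% to 65.0% | 15.7% to 70.3% | 11.2% to 65.8% | 9.6% to 63.8% |
| Minimum power | 62.6 | 64.2 | 62.9 | 63.0 |

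The range common to all four runs from 15.7% to 63.8%, that is, about 16% to 63%.

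**Variations**
- UPA lower by 23 points: all four methods are under 80% for LNG ECx2 rates of about 37% to 84%.
- Difference detectable with 80% power (pooled, UPA higher): 23.7 points at an LNG rate of 10%, 26.7 at 20%, 27.9 at 30%, 27.8 at 40%, 26.6 at 50% and 24.5 at 60%.
- One-sided 5%: 74% to 75% at 40% v 63%. The shortfall narrows to LNG rates of about 18% to 56% (pooled) or 26% to 60% (unpooled).
- 31 and 73 women, the numbers left if the dropout allowances are used up: 58% at 40% v 63% (pooled).
- 70 v 80: at least about 81% at every rate by all four methods. Seventy is Part 1's total for both LNG arms. The documents do not show whether it was used here.

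**The case against.** The strongest reply is that the figure can be recovered from the document's only stated rate. At 10% v 33%, arcsine gives 81.7% and unpooled Z 88.3%. By arcsine a 22-point difference gives about 79%, so 23 is the first whole-point difference to pass 80%. Part 1's own 31 per arm at 10% v 40% behaves the same way: 79.3% pooled, 81.5% arcsine, 82.8% unpooled. The power sentence also speaks of groups in both parts and follows a mention of four regimens, so LNG ECx1 may have been the intended reference.

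That is a plausible origin, but it does not rescue the sentence. The 10% is an LNG ECx1 rate, while the sentence that names the test names LNG ECx2. Even at 10%, the exact calculation for the named test falls just short. If LNG ECx1 was meant, the plan needs to say so.

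Three further points stand in part:
- The 40% rate is constructed, and the investigators believe the true Part 1 difference is larger. A 50-point difference would put LNG ECx2 at 60%, where power is 70% to 75%. The claim is met only above about 64% to 70%, depending on method.
- A one-sided test narrows the problem range, but a chi-square test is not one-sided.
- The analysis is descriptive and no conclusion of no difference is planned. This limits the consequence but does not make the figure right.

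**Conclusion.** The concern holds. As written, the power statement is unconditional, and the stated design does not deliver it over most rates. With a two-sided 5% test, independent groups of 35 and 80, and UPA ECx2 higher by 23 points, power is under 80% by all four methods for LNG ECx2 rates of about 16% to 63%, with a minimum of about 63%. The claim is true at some rates, chiefly very low or high ones, but the plan does not say that it relies on them. Severity is minor: no sample size and neither primary analysis depends on the figure.

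**What to change.** Replace the clause with one that states the pair, reference rate, direction, sidedness and method. For example: *With 35 and 80 women and a two-sided 5% test (pooled Z), power to detect a 23-point higher rate on UPA ECx2 is about 63% to 78% for LNG ECx2 rates of 10% to 60%; the difference detectable with 80% power is about 24 to 28 points.* The method must be named, because at a 10% rate the four methods span 78% to 88%. Deleting the power claim would serve equally well for a descriptive analysis.

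Before restating it, check which LNG arm, reference rate and LNG group size (35 or 70) were entered in the calculation, and correct the UPA ECx2 label. In either case, report the difference with its 95% confidence interval. At 40% v 63% the half-width is 1.96 × 0.0988 = 0.194, or about 19 points.

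The cost is one sentence, with no additional women and no change to either primary analysis. The stated power becomes less favourable.

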Data Analysis & Sample Size: To ensure equality between treatment arms at baseline, we will compare participant demographics using t-test or chi-square test and descriptive statistics, such as mean, median and percentages within each group will be reported. The primary outcome analysis will compare the proportion of women with a delay in follicular rupture of at least 6 days (yes/no) between obese women taking UPA ECx1 versus ECx2 using McNemar's test. Only the women who have completed the two treatment cycles will be included in this portion of the analysis. Although we expect absence or ignorable "period" effect, we will further describe the difference between ECx1 and ECx2 with odds ratios using the generalized estimation equation adjusted for period and any other confounders using all available data. We will check the accuracy of our findings against a normal BMI control group using standard dosing, ECx1 using chi-square test. Follicle rupture will be defined as the disappearance of or >50% reduction of size of the leading follicle. Confirmation of ovulation will be supported by LH, P4, and E2 levels. Descriptive statistics will be utilized to report LH and P levels [mean (standard deviation)], follicular diameter [median (range)], and cycle day [median (range)] on the day of EC ingestion during the treatment cycle. Additionally, inhibition of follicular rupture will be plotted by LH status (no surge, start of LH surge, or after LH peak) [2,17] for each cycle as well as mean LH, P4, and E2 levels over time and the time of treatment to follicular rupture.

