A sample size of 73 will achieve 80% power to detect a 20% difference in the proportion of cycles that demonstrate at a delay in follicular rupture (yes/no) using a two-sided McNemar test with a Bonferroni-adjusted 2.5% significant level. We estimate that 40 women will choose to participate in Aim 2 after completing Aim 1 studies and plan to screen an additional 58 women to account for screen failures for a total enrollment of 80 women to account for drop out. We believe that the difference between groups will likely be smaller given the clinical information (50% or less). We have chosen a difference of 20% in which to base our sample size calculations. We have consciously chosen not to enroll an adequately sized normal BMI group to detect the same amount of difference (20%) given that there are published PK/PD standards. We are utilizing this group to verify the accuracy of our findings under our environment, the targeted 10 total number of subjects (after 12 screening) in the control arm would achieve the 80% power to detect 47% difference in follicular rupture given the 73 of women taking UPA ECx1 using two-sided Z test with 2.5% significance level. The total number of subjects in the control arm was chosen as a convenience sample but this number of subjects should supply us with an adequate amount of data to ensure that our PK/PD results are similar to published values in a normal BMI cohort.

Protection of human subjects:

1. Risks to Subjects

Human Subjects Involvement and Characteristics

Reproductive-aged (18-35 year old), ovulatory, healthy women with a normal or obese BMI with no contraindications to the study medications and not at risk for or seeking pregnancy will constitute the target population for this study.

All enrollment and clinical evaluations will be performed at OHSU in Portland, Oregon. Serum samples will be prepared at OHSU and analyzed at the ONPRC Endocrine Core Laboratory under the direction of [name]. De-identified pharmacokinetic data will be analyzed by our consulting pharmacokinetic specialist, [name].

Sources of Materials

The sources of research material for the clinical portion of this proposal will be new specimens obtained purely for this research protocol. The study investigators and/or research assistants/nurses will perform all study procedures.

Potential Risks

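### Part 2 tests its only named primary comparison at a Bonferroni 2.5%; Holm, or testing it first at 5%, would hold the same 5% family-wise error with less loss of power

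*Combined protocol and SAP*

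**What the plan says.** Under Part 2, Data Analysis & Sample Size, the analysis paragraph names one primary comparison: "The primary outcome analysis will compare the proportion of women with a delay in follicular rupture of at least 6 days (yes/no", and this is made "between obese women taking UPA ECx1 versus ECx2 using McNemar's test". The same paragraph adds a chi-square comparison with normal-BMI women on the standard dose, as a check on accuracy. It gives no significance level and no testing order.

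The levels appear only in the sample-size paragraph that closes Part 2. For the primary: "A sample size of 73 will achieve 80% power to detect a 20% difference in the proportion of cycles", by a "two-sided McNemar test with a Bonferroni-adjusted 2.5% significant level". For the normal-BMI group, 10 women are set against 73 obese women on the standard dose, with 80% power for a 47-point difference, "using two-sided Z test with 2.5% significance level". On that group's purpose the plan says: "We are utilizing this group to verify the accuracy of our findings under our environment". It adds that the group is a convenience sample and was knowingly not sized for the 20-point difference.

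The Part 2 Specific Aim, which also opens the protocol, has two limbs. The obese-normal comparison comes first and dose escalation second.

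**The concern.** Part 2 seems to divide a 5% error rate equally between the comparison it calls primary and a check on a small convenience group. Under plain Bonferroni the primary is held to 2.5% whatever the other test shows. Other procedures hold the same 5% family-wise error and reject at least as often on the primary, so the plan may be giving up power on its main question for nothing.

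The margin matters because of the analysis set: "Only the women who have completed the two treatment cycles will be included in this portion of the analysis". With 80 women enrolled and 73 pairs required, only 7 can be lost before the stated power is missed.

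**Working it through.** **Inputs from the plan.** 73 pairs, difference d = 0.20, power 80%, two-sided 2.5% (primary); 10 controls against 73 obese women, 47 points, 80% power, two-sided 2.5% (control comparison).

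**Input not in the plan.** The proportion of discordant pairs, D, which any McNemar calculation needs. It is back-solved below and then varied.

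**1. Which tests share the 5%?** The plan does not say. These two are the only tests given 2.5%, and they sum to 5%. Part 1 has its own 5%, and the exploratory LNG-UPA comparison is quoted at 5%. The stated 47 points also fits a 2.5% test. With 10 against 73, the difference detectable with 80% power at 2.5% is about 45 to 48 points for obese rates of 20% to 80%; at 5%, 47 points would have about 86% power or more. The pairing is therefore a well-supported inference, but still an inference.

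**2. Reproduce the 73.** With the usual paired-proportions formula,

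n = [z(1−α/2)·√D + z(power)·√(D − d²)]² / d².

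At α = 0.025, z = 2.241; for 80% power, z = 0.842. Solving for n = 73 gives D = 0.318 (0.3184 unrounded):

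(2.241 × 0.5643 + 0.842 × 0.5276)² / 0.04 = (1.709)² / 0.04 = 73.

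The 73 cannot be checked from the plan's inputs alone, but it is attainable.

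**3. Primary power if tested first at 5%.** With the same 73 pairs,

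(0.20 × √73 − 1.960 × 0.5643) / 0.5276 = (1.709 − 1.106) / 0.5276 = 1.143,

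so power is 87.3%. Other versions of the test (unpooled, enumerated asymptotic, continuity-corrected, mid-p, exact), each calibrated to 80% at 2.5%, give 86.9% to 88.5%. At 5% and D = 0.318, 80% power needs about 61 pairs, so 80 − 61 = 19 losses could be absorbed in place of 7. Equally, with 73 pairs the 80% target holds up to D = 0.384.

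**4. Sensitivity to D** (73 pairs, d = 0.20):

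| Assumed D | Power at 2.5% | Power at 5% | Gain (points) |
|---|---|---|---|
| 0.20 | 96.1% | 98.1% | 2.0 |
| 0.25 | 90.0% | 94.4% | 4.4 |
| 0.30 | 82.7% | 89.4% | 6.7 |
| 0.318 | 80.0% | 87.3% | 7.3 |
| 0.35 | 75.4% | 83.8% | 8.4 |
| 0.40 | 68.6% | 78.3% | 9.7 |
| 0.50 | 57.2% | 68.3% | 11.1 |

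**5. Primary power under Holm.** The primary is rejected if p ≤ 0.025, or if p ≤ 0.05 and the control test has p ≤ 0.025. Treating the tests as independent (approximate, since both use the obese standard-dose data), power is 0.800 + 0.073 × (control power at 2.5%).

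- No obese-normal difference: 0.800 + 0.073 × 0.025 = 0.802, about 80%.
- Control power 78.4% (47 points, taken as 26.5% against 73.5%): 0.800 + 0.073 × 0.784 = 0.857, about 86%.

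**6. Effect on the control comparison,** same rates and independence. Its power is 78.4% at 2.5% and 86.1% at 5%.

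- Bonferroni: 78.4%.
- Holm: 0.784 + 0.800 × (0.861 − 0.784) = 0.846, about 85%.
- Fixed order, primary first: 0.873 × 0.861 = 0.752, about 75%.

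**The case against.** The best defence is that nothing is broken. Bonferroni controls the family-wise error, and the plan sizes the primary after the adjustment. A reader might infer that the split leaves the primary underpowered; the plan's figures do not support that, since it claims 80% at 2.5%. This stands, and it limits the point to efficiency.

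Second, the equal split may be deliberate. The Part 2 aim names the obese-normal comparison first, and the Part 2 hypothesis also begins with it. A reader might infer from the convenience sample and the single primary label that the plan plainly ranks the control comparison second, so that a fixed order merely follows its hierarchy. The documents point both ways. A fixed order would leave the obese-normal comparison non-confirmatory whenever dose escalation shows no benefit, even if obese women respond worse to the standard dose. This also stands: the fixed order is partly a choice of priority for the sponsor. It is no argument against Holm, which treats the two tests alike.

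Third, raising the primary's level in an open-label trial whose normal-BMI enrolment is already complete could look like a late loosening. That is a fair condition on timing, and the fix carries it.

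**Conclusion.** The point holds as an improvement in efficiency. Plain Bonferroni is valid but needlessly costly on the inferred family of two tests, because Holm never rejects less at the same 5% error.

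The size depends on the remedy. A reader might credit any replacement for Bonferroni with a rise from 80% to 87%. That figure belongs to the fixed order alone, and to a discordant proportion of 0.318 that the plan does not state; over 0.20 to 0.50 the gain is 2 to 11 points. Holm gives the primary between about 80% and about 86%, depending on whether obese and normal-BMI women really differ.

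The conclusion rests on three assumptions: the pairing of the two 2.5% levels, the back-solved discordance, and approximate independence wherever the tests are combined.

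**What to change.** Name the two tests that share the 5%, and state the rule in the Part 2 analysis paragraph as well as in the sample-size paragraph. Date the change before any outcome data are examined, because the trial is open-label.

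- **Minimum:** replace Bonferroni with Holm. Test the smaller of the two p-values at 2.5% and, if it is significant, the other at 5%. This has no statistical downside and suits a sponsor who wants both limbs of the aim to keep equal standing.
- **Alternative:** because one comparison is called primary, test single against double dose first at two-sided 5%. Test the obese-normal comparison at 5% only if the first is significant; otherwise report it as an estimate with its confidence interval. The cost is that the obese-normal comparison is not confirmatory when the primary fails, and loses about 3 points of overall power (78% to 75%).

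Under either rule, state the discordant proportion assumed for the McNemar calculation so that the 73 can be checked. The change is a paragraph of text, repeated in brief in the sizing section; it needs no additional women or visits.
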